Individuals who express interest in the study, will be screened for eligibility by the study coordinator or a research assistant via phone. If their answers to the IRB approved phone screen indicate that they may be eligible for the study, the parent/guardian will be asked to complete the Social Responsiveness Scale – Second Edition (SRS-2) online via RedCap, a secure online data capture system. The study coordinator will send a link to complete the SRS-2 electronically to the parent/guardian via REDCap. An online consent statement will appear, prompting parents to indicate their agreement to participate in the online questionnaire portion of the study. If the parent/guardian indicates their agreement, the data capture system will proceed to the SRS-2. After completing the SRS-2, eligible participants based on inclusion and exclusion criteria will either be scheduled to speak with a study clinician via phone to obtain informed consent (and assent as necessary) prior to completing further screening and baseline study procedures via virtual visit.

Photobiomodulation for ASD in ADHD

Study staff will send the consent form and assent form (when applicable) to subjects in PDF form ready for Adobe eSignature via email with a brief statement (email template submitted) explaining why they are receiving this form and further instructions. Study staff will schedule a time for the subject and their parent(s)/guardian to meet with a study clinician via phone or secure Zoom video call to complete the consent. The study clinician will have a conversation with the subject and their parent(s)/guardian to obtain consent in the usual fashion: review the consent form, review the inclusion and exclusion criteria, review risks and benefits of the study, review alternatives to participation, and answer any questions subjects and their parent(s)/guardian may have. If the subject and their parent(s)/guardian decide to participate, they will sign the consent form and assent form (when applicable) using Adobe eSignature. The study clinician will also sign the consent form using Adobe eSignature prior to beginning any study procedures. Subjects will be sent a copy of the signed form by email for their records.

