This study is a 10-week, open-label, single treatment group designed to investigate efficacy, safety and tolerability of tPBM in treatment of ATs in youth with ADHD. The study may take up to 14 weeks from enrollment (allowing up to 4 weeks to schedule and complete initial screening and baseline visit).

Photobiomodulation for ASD in ADHD

If a potential subject's clinician ascertains that the patient has an interest in study participation, the clinician will offer contact information for the study to the patient and/or their parent/guardian. The patient and/or their parent/guardian can then contact the study coordinator for more information on the study. If the patient's physician is a member of study staff, the patient and his/her family will also be offered the opportunity to speak with another study physician who is not their treating clinician to review study details and consider participation. Clinical records are not scanned in order to recruit subjects.

After providing written informed consent, all subjects will complete a clinical diagnostic interview via a virtual visit with a board-certified study clinician to assess eligibility. A study clinician will complete the Reproductive Potential Form. All subject's parent/guardian will be administered an assessment battery including a brief demographic interview and the SRS-2.

If an additional family member of the subject is available, we will ask that family member to independently complete an SRS-2 form. Both forms will be scored and the form with the higher score will be used to determine subject eligibility in order to reduce the possibility of under-recognition of social impairment.

Study clinicians will complete a chart note at Weeks 0, 1, 2, 3, 4, 6, and 8. For a complete schedule of assessments, please refer to Table 1. The screening process may take place over multiple days, as necessary.

All data will be collected and entered into Research Electronic Data Capture (REDCap), an electronic data capture system that streamlines data collection and ensures data integrity. REDCap software allows researchers to design and implement study surveys electronically for collecting, storing, retrieving and manipulating data.

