1.1. Study Visits

Study visits will occur entirely via TeleHealth or Zoom, which is maintained by Partners HealthCare. In the event that TeleHealth or Zoom malfunction or a subject loses access to a device compatible with these platforms at scheduled time, the study visit will be rescheduled. The study involves screening, baseline, and a series of clinical monitoring and follow up visits.

Screening Process (Week 99)

The screening process includes the following components:

- Subjects will virtually meet with a study clinician for a psychiatric evaluation and review of medical history.
- The study clinician will ask the participant about his or her symptoms of autism spectrum disorder.
- The study clinician will ask the participant about his or her symptoms of ADHD.
- The study clinician will ask the participant and their parent/guardian questions regarding their child's reproductive potential. If deemed necessary, female participants of childbearing potential will complete a urine pregnancy test. If a participant has a positive pregnancy test, she will not be able to take part in the study. The study doctor will inform the participant and discuss the clinically appropriate course of action. The participant will be offered 3 follow-up visits.
- We will ask the participant's parent/guardian complete three observer-rated questionnaires about their child's ASD symptoms (SRS-2, CBCL, MGH-SECS). These questionnaires will take approximately 30-40 minutes to complete.
- We will ask the participant's parent/guardian to complete a brief demographic interview collecting information regarding socioeconomic status and history of head injury or trauma. This will take about 5-10 minutes to complete.
- Optional: if an additional parent/caregiver is available, we will ask them to complete one to three observer-rated measures on REDCAP.

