We anticipate that subjects may enter this trial following completion of/withdrawal from other protocols in our office, and that there may be procedural overlap. So as to not burden subjects/parents/guardians with redundant time commitments, we will use the following diagnostic data previously collected: If a subject has completed an evaluation with one of the study clinicians in the three years preceding their entrance to the study, they will not be asked to repeat these overlapping diagnostic procedures. We will use the study diagnostic data previously collected so as to not burden the subject with redundant time commitments. However, the study clinician will review the interval time period to assess for clinically significant medical or psychiatric history to ensure that the subject meets appropriate study entrance criteria.

Study participants and/or their legal guardians may request the results of their cognitive testing. In this case, the subject will receive a letter providing a basic interpretation of the results and referring them to the department's supervising neuropsychologist for any questions or concerns.

Photobiomodulation for ASD in ADHD

The following assessments will be performed at the Screening Visit:

- CGIs
- GAF
- CTAE
- Concomitant Medications
- Demographic Interview
- SRS-2 (Pre-Screening)
- CBCL
- MGH-SECS-I
- MGH-SECS-C
- BRIEF-P

Study Treatment Phase (Weeks 0-8)

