The treatment device is classified as an “Exempt” device in accordance with the requirements of the international standard EN 62471 – Photobiological safety of lamps and lamp systems and, when used correctly, the output is less than the maximum permissible exposure (MPE) no special controls are needed for the environment it is to be used in. At the time of study implementation, the staff will be provided training on basic safety procedures relative to the use of the device. The staff will then virtually instruct the subject’s parent/guardian on the administration of the tPBM such that the headband is appropriately placed. The delivery of the tPBM is expected to last 10-40 minutes total (simultaneous application on the left and right forehead). The subject will be asked to rest for five minutes after the delivery of tPBM. Sites of application will be inspected at each study visit.

Subjects will be instructed to administer the treatment sessions daily for eight weeks, with each session lasting 10-40 minutes. Subjects will be instructed to contact the investigator or a member of his staff at any time between visits concerning adverse events or worsening of symptoms.

Following assessments will be performed at the Baseline Visit:

- CGI
- GAF
- CTAE
- Concomitant Medications
- ADHD-SC

Study Treatment: Virtual Clinical Monitoring Visits (Weeks 1-6)

There are 5 monitoring visits scheduled at Week 1, Week 2, Week 4 (Midpoint), Week 6, and Week 8.

Participants will be prescribed to administer study treatments at home daily for a period of 8 weeks. Study visits will have a visit window of +/- 3 days to facilitate scheduling.

During the visits, the participants will be asked questions about the symptoms of ADHD and ATs and general health in addition to any present side effects or changes in their medications. At weeks 2, 4 (Midpoint), and 6 the participant will be asked to fill out questionnaires.

Following assessments will be performed at the Week 1, Week 2, Week 3, and Week 6 Visits:

- CGI
- GAF
- CTAE
- Concomitant Medications
- TSRQ

Following assessments will be performed at the Midpoint (Week 4) Visit:

- CGI
- GAF
- CTAE
- Concomitant Medications
- ADHD-SC
- SRS-2

- BRIEF-P
- TSRQ
- CBCL

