1.2.2.1. Parent-Rated Behavioral Measures

(Administered at screening and/or baseline, midpoint, endpoint and follow up study visits)

- Social Responsiveness Scale-Second Edition (SRS-2; (46)): a 65-item rating scale completed by the parent used to measure the severity of autism spectrum symptoms as they occur in natural settings.
- Behavior Rating Inventory of Executive Function-Parent (BRIEF-P;(47)): a 78-item rating scale to assess level of executive function deficits.

- Child Behavior Checklist (CBCL;(48)): is a parent-report questionnaire that evaluates maladaptive behavioral and emotional problems, both internalizing and externalizing, in children ages 6-18.

(Administered at baseline and endpoint)

- MGH Social-Emotional Competence Scale [Informant-Rated] (MGH-SECS-I): This is a 37-item scale that assesses social competence and abilities on a Likert scale from 0 to 6.

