Considering the open-label single group design, we will rely on comparisons of the participants' performances at baseline prior to the initiation of treatment relative to their scores at the last assessment (completion/drop-visit). This design largely protects against the bias introduced by confounding factors. That is, since the same participants are tested on multiple occasions, all static confounding factors are perfectly balanced, and can have no impact on the findings. However, dynamic confounding factors may have impact on the findings (ex. Bias) and can still result from time-varying factors that are not associated with the outcomes, which is an inherent limitation of an open-label design. However, we are confident that any such factors will have a minimal impact on this study considering the duration of the trial. Since we are following subjects over a short period, missing data are not expected to impact our analyses such that standard statistical analyses will be employed. Specifically, we will employ longitudinal mixed-effects regression models (RM) with random effects for the subjects using Stata 16.0 (49). This approach has several advantages over traditional methods such as repeated measures ANOVA or MANOVA [19]. Unlike traditional methods, mixed effects RMs do not exclude subjects with missing data, can incorporate covariates (both time-varying and not) (Gibbons 1993), and can estimate the size and significance of variables predicting group outcome after accounting for individual variation in outcome. The RMs will use robust standard errors to account for the repeated measures on each subject. We will test binary data using mixed-effects logistic RMs, count data with mixed-effects Poisson RMs, and normally distributed data with mixed-effects linear RMs. Each model will predict outcome score from study visit (continuous predictor).

Primary Objective: posits that tPBM for the treatment of ATs in youth with ADHD will be safe and effective in the treatment of ATs in youth with ADHD. Our primary measure of efficacy will be the SRS-2 Total raw score which is collected at baseline, midpoint, and endpoint. The psychometric properties of the SRS have been well established as a valid measure to assess for autistic traits and can distinguish autism from other neuropsychiatric conditions (20, 50). We will examine the change in SRS-2 Total raw score over time using a mixed-effects linear RM. Our

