2. REFERENCES

3. ATTACHMENTS

3.1. Table I. Study Schema

Weeks	99	0	1	2	3	4	6	8	10
Visits	Screen	Baseline	W1	W2	W3	MP	W6	EP	FU
Informed Consent	X								
tPBM Device Subject Training	X	X							
tPBM Treatment - 10 min/day		X							
tPBM Treatment - 20 min/day			X						
tPBM Treatment - 30 min/day				X					
tPBM Treatment - 40 min/day					X	X	X	X	
Diagnostic Assessments									
Inclusion/Exclusion Criteria	X								
Psychiatric Evaluation & Medical History	X								
Physiological Procedures									
Virtual Examination of Exposure Sites		X	X	X	X	X	X	X	
Urine pregnancy test	X*	X*		X*		X*	X*		
Clinician-Rated Assessments									
Pregnancy Potential/Monitoring Form	X	X		X		X	X		
MGH-SECS-C	X							X	
ADHD-SC		X				X		X	X
CGIs	X	X	X	X	X	X	X	X	X
CTAE	X	X	X	X	X	X	X	X	X
Concomitant Medications	X	X	X	X	X	X	X	X	X
GAF	X	X	X	X	X	X	X	X	X
Progress Note		X	X	X	X	X	X	X	X
Parent-Rated Assessments									
Demographic Interview	X								
SRS-2	X					X		X	X
MGH-SECS-I (Observer)	X							X	
CBCL	X					X		X	
BRIEF-P	X					X		X	
Self-Reported Assessments									
TSRQ			X	X	X	X	X	X	X

*If deemed necessary by the clinician-rated pregnancy potential/monitoring form

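### The schedule has no Week 0 SRS-2 and the plan names no analysis baseline; if the screening score that admits a child is used, regression to the mean biases the uncontrolled change towards benefit

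*Combined protocol and SAP*

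**What the plan says.** Under VI. Biostatistical Analysis, Primary Objective: "Our primary measure of efficacy will be the SRS-2 Total raw score which is collected at baseline, midpoint, and endpoint". The model regresses the total raw score on study visit as a continuous predictor, and the subscales are handled in the same way.

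The schedule does not match:

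- **Baseline Visit (Week 0).** The list that opens "Following assessments will be performed at the Baseline Visit" contains CGI, GAF, CTAE, concomitant medications and ADHD-SC. It has no SRS-2.
- **"3.1. Table I. Study Schema".** The SRS-2 row is marked at Screen, Week 4, Week 8 and Week 10. The Week 0 cell is empty, whereas the ADHD-SC row is marked there.
- **1.2.2.1.** The timing is left open: "Administered at screening and/or baseline, midpoint, endpoint and follow up study visits".

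The forms described before treatment are:

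- **IV. Subject Enrollment.** An online parent or guardian form precedes the main informed consent: "After completing the SRS-2, eligible participants based on inclusion and exclusion criteria will either be scheduled to speak with a study clinician".
- **Study Design.** After consent, "All subject's parent/guardian will be administered an assessment battery including a brief demographic interview and the SRS-2". The Screening Process text also has the SRS-2 among the parent questionnaires, and the screening list labels it as pre-screening.
- **Study Design.** An additional family member may complete a form, and the higher of the two scores decides eligibility.

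The severity criterion is met by a raw SRS score of at least 75 or a CGI-AT severity of at least 4. Section VI concedes that time-varying factors can bias an open-label comparison, but expects little effect because the trial is short.

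**The concern.** The primary test compares change with zero in a single arm. That is a fair null only if the expected change without a treatment effect is zero.

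A child admitted because a noisy score was high tends to score lower on re-measurement. On the SRS-2 lower is better, so this fall looks like improvement. If the admitting score is also the baseline, the estimated benefit can be inflated and the false-positive rate can exceed 5%. A short trial does not prevent this, because regression to the mean needs only a second measurement.

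The documents also leave open whether the online form and the post-consent form are separate and which of them is the baseline. That choice could be made after data are seen.

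**Working it through.** **1. The plan's own figures.** Inputs from Sample Size: n = 60, r = 0.5, SD = 1, two-sided alpha 0.05. The SD of change is √(2(1 − 0.5)) = 1. For 0.37 SD the noncentrality is 0.37 × √60 = 2.87, and power on 59 df is 80.5%. For 0.8 SD it exceeds 99.9%. Enrolment is 60/(1 − 0.33) = 89.6, rounded up to 90. All stated figures reproduce, so the power calculation is not in error.

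**2. Age of the baseline.** Study Design allows up to 4 weeks from enrolment for screening and baseline. Subject Enrollment defines enrolment as signing informed consent. The online SRS-2 comes before that signature, so the window does not limit how old that form may be.

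**3. Expected change with an inert device.** The documents give no SRS-2 mean, SD or reliability for the referral pool. The assumptions are therefore normal scores, a test-retest correlation (stability) ρ of 0.5 to 0.9, a CGI-AT to SRS correlation of 0.5, and the screening score used as baseline.

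Simplest case: the SRS-2 alone gates entry, at the pool mean, with ρ = 0.7.

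- Expected drop = (1 − ρ) × φ(0)/(1 − Φ(0)) = 0.3 × 0.798 = 0.239 pool SD.
- Variance of change = 0.3² × (1 − 0.798²) + (1 − 0.7²) = 0.033 + 0.510 = 0.543, so the SD is 0.737.
- dz (mean change divided by SD of change) = 0.239/0.737 = 0.325. With n = 60 the test rejects about 70% of the time.

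Entry by either route, as the inclusion criteria state, was simulated with both cuts at the same distance from the referral mean (4 million draws per cell). Rejection comes from the noncentral t, n = 60, two-sided 5%:

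| Stability | Cut −1 SD | Cut 0 | Cut +1 SD |
|---|---|---|---|
| 0.5 | 6% (dz 0.04) | 20% (dz 0.15) | 70% (dz 0.325) |
| 0.7 | 6% (dz 0.03) | 14% (dz 0.11) | 50% (dz 0.26) |
| 0.9 | 5% (dz 0.02) | 8% (dz 0.07) | 21% (dz 0.15) |

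If the CGI-AT route is looser than the SRS route, rejection at stability 0.7 is close to nominal: 7%, 6% and 5% for SRS/CGI cuts of +1/0, +0.5/−0.5 and 0/−1 SD.

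**4. The mixed model does not remove it.** With complete data at Weeks 0, 4 and 8 and a random intercept, the fitted slope is (−4y₀ + 0·y₄ + 4y₈)/32 = (y₈ − y₀)/8. The fitted 8-week change is therefore y₈ − y₀. Simulating that model with robust standard errors at stability 0.7 gave about 5, 14 and 53% for the three equal cuts.

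**5. A separate Week 0 baseline.** In the same cells, with constant stability, the expected change is 0.00 and the paired test rejects 5% of the time.

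**The case against.** The strongest reply is that Table I has one pre-treatment SRS-2 column, so the screening score is plainly the baseline, as in many open-label studies. That reading is natural, but it does not dispose of the point: it is the case in which the bias arises.

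A second reply is that the CGI-AT route dilutes the effect. This stands in part, and the cells near 5% show it. It cannot be assumed, because Subject Enrollment puts the SRS-2 before the clinician contact and does not say whether a child below 75 goes on to a CGI-AT rating. Equally, the text refers to the full eligibility criteria, so SRS-only entry cannot be assumed either.

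A third reply is that the plan already admits the limits of an open-label design. It does, but it then calls the impact minimal and does not mention regression to the mean.

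Some stronger readings are tempting and should be resisted:

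- A reader might infer that no pre-treatment SRS-2 is collected. One is, at screening.
- A reader might infer that any relative's form could serve as baseline. The documents name the parent or guardian as rater, and the higher-score rule is stated for eligibility only. What stays open is which form, and whether the same parent rates throughout.
- A reader might set the null drop in enrolled-baseline SDs (0.42 in the stability 0.5, +1 SD cell) against the planned 0.37 SD. The scales differ. The planned figure goes with a change SD of 1 and so is also a dz, and the comparable value in that cell is 0.325. Its 70% rejection is below the planned 80%.

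**Conclusion.** The point holds in conditional form. The primary analysis relies on a baseline SRS-2 that the Week 0 schedule does not contain. A plan followed as written draws that baseline from screening, where a high score is an entry route. If the admitting score is used, the bias runs towards benefit and nothing in the design or the model removes it.

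A reader might go on to infer that a positive result would be mostly artefact. The documents do not support that. With entry by either route and equal cuts, the illustrations run from about 5% to 70%; the spread comes from assumed cuts, stability and CGI-AT correlation. Confidence is high for the schedule gap and the direction of the bias only. This should be fixed because it touches the primary endpoint and the remedy is small.

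**What to change.** 1. Add one parent SRS-2 at Week 0, after eligibility is settled and before the first treatment, to the Week 0 list and Table I.
2. Define it as the baseline for the primary and subscale models. Use screening forms for eligibility only, and state whether the online and post-consent forms are separate.
3. Have the same parent or guardian rate at Weeks 0, 4 and 8 and at any exit visit.
4. In Section VI, replace the statement that time-varying factors will matter little with one saying that uncontrolled pre-post change can include residual regression to the mean and expectancy effects.

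The cost is one more 65-item online form per family in the existing REDCap system, a few text edits and probably a smaller observed change. The remedy is not complete. If stability fades with time (assumed correlations of 0.8 from screening to Week 0, 0.7 from screening to Week 8 and 0.75 from Week 0 to Week 8), false positives with the Week 0 baseline are about 6% at a cut of 0 and 11.5% at +1 SD, against 14% and 50% with the screening score. Expectancy effects remain.

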Aforementioned proof-of-concept study was blessed with a fast pace of recruitment, with 10 participants over a period of 18 months, despite its demanding nature for our patients. Even faster and more efficient recruitment along with a less demanding schedule for our patients is

Photobiomodulation for ASD in ADHD

possible. Telemedicine substitutes for face-to-face office visits through a remote, two-way video-conference through secure Internet access. Telemedicine use in the clinical setting has successfully provided specialist advice with favorable patient outcomes, satisfaction, and costs (38-41). Clinical trials are the gold standard for evaluating new therapeutic opportunities in medicine, efforts aimed at improving their efficiency are needed to facilitate patient participation in a manner that reduces dropout, and Telemedicine may offer such opportunity.

We propose an open label trial to assess the safety and efficacy of tPBM in improving ATs in ADHD youth with comorbid ATs. Eligible participants will be youth with adequately treated ADHD who present with comorbid ATs of at least moderate severity. Participants will receive tPBM daily for 8 weeks. Participants who meet eligibility criteria will be mailed the tPBM device. They will be able to administer the treatment in the comfort of home, at scheduled intervals. Accurate application of tPBM, its safety, and efficacy will be assessed during regular scheduled meetings with study clinician. These meetings will all be conducted via telemedicine with HIPAA compliant communication technology. Safety of and treatment response to tPBM will be monitored by parent- and clinician-rated measures during regularly scheduled visits. Our study will address the question whether tPBM is effective for the treatment of ATs in youth with ADHD, and whether it is acceptable among our patients.

Certain aspects of tPBM render it a feasible intervention. It can be delivered at home. It does not require ingestion of any substances. It is possible that the exposure to tPBM might be more acceptable than use of medications among some minority groups. This intervention does not require providers with specific cultural expertise or second language proficiency.

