1.2.1. Clinician-Rated Assessments

1.2.1.1. Clinician-Rated Behavioral Measures

(Administered at all visits)

- Clinical Global Impression Scale (CGI; (43)): The CGI is a measure of illness severity, improvement, and efficacy of treatment. The score for severity ranges from 1 (normal, not at all ill) to 7 (among the most extremely ill subjects). Improvement ranges from 1 (very much improved) to 7 (very much worse). The effectiveness index measures to what extent the subject is experiencing therapeutic effects in conjunction with the level of adverse events they are experiencing. CGI scales will be used for the assessment of ADHD and ATs
- Global Assessment of Functioning Scale (GAF; (44)): composite rating of an individual's overall level of functioning (1= worst to 100 = best).

(Administered at baseline and/or screening, midpoint, and endpoint)

- MGH Social-Emotional Competence Scale [Clinician-Rated Measure] (MGH-SECS-C): This is a 37-item scale that assesses change in the frequency and severity of core and associated symptoms of ASD.
- ADHD Symptom Checklist (ADHD-SC) assesses each of the individual symptoms of ADHD based on the DSM (0-3 on a scale of severity)

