The primary outcome measure for this open-label, single arm trial will be reduction in ASD symptoms as measured by change in SRS-2 total raw score from baseline to endpoint. We base our power calculations on a two-sample paired-means test. We assessed power in terms of Cohen's definition of medium and large effect sizes because they are indicative of clinically meaningful differences. These effect sizes correspond to 0.5 and 0.8 standard deviation (SD) changes from baseline to endpoint, respectively, and have been widely accepted in the fields of psychiatry and behavioral sciences. The following power calculations assume a two-tailed test, an alpha level of 0.05, a moderate strength correlation between baseline and endpoint scores ($r=0.5$), a standardized scale of measurement (i.e. mean of zero and standard deviation of 1.0), and a sample size of 60 subjects. We have 99.9% power to detect a large effect size (0.8 SDs) from baseline to endpoint and we can achieve adequate (80%) power to detect effect sizes as small as 0.37 SDs. Our goal is to have 60 subjects exposed to the treatment. In anticipation of a 33% attrition rate, we will need to enroll 90 subjects to ensure 60 subjects are exposed.

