dependent variable will be raw score on the SRS-2 Total scale and our predictor will be study visit (continuous). Secondary measures of efficacy for the treatment of ATs will be the SRS-2 subscales which include Awareness, Cognition, Communication, Social Motivation, and Restricted Interests and Repetitive Behavior. These subscales will also be analyzed using mixed-effects linear RMs predicting subscale score from study visit (continuous). Safety and tolerability will be assessed by examining adverse events reported throughout the trial.

Secondary Objective: posits that tPBM will be effective in the treatment of ADHD with ATs. The measure of efficacy for this objective will be the ADHD-SC which is collected at baseline, midpoint, and endpoint. We will examine the change in ADHD-SC score over time using a mixed-effects linear RM. Our dependent variable will be ADHD-SC score and our predictor will be the study visit (continuous).

Accountability/Investigational Product Control

U.S. federal law and ICH Guideline E6 § 5.14 requires that all investigational medical devices be strictly controlled. All study devices must be kept in a secured area at the clinical sites in compliance with all applicable FDA (U.S. sites) regulations.

The Principal Investigators or designated study site personnel who verify the receipt of the devices/device accessories must complete the Device/Accessories Acknowledgment Form and fax a copy to Niraxx, Inc. Device Accountability and Acknowledgment Logs will be maintained at study site. These logs will list all equipment received, the receiving date, the serial number of each device. Study site personnel will initial the log each time the device is used. Niraxx device use will also be recorded on the appropriate CRF.

Malfunctioning devices and device accessories, including all components, will be returned to Niraxx, Inc. for investigation, at Niraxx, Inc. expense.

VI. RISKS AND DISCOMFORTS

All adverse events will be recorded from the time of Informed Consent through study completion, or termination. The Adverse Event CRF must be completed and submitted to the IRB, as required. Regulations for adverse event handling and reporting contained in the FDA and ICH Guidelines will be adhered to.

Consideration of Adverse Events will hereafter consist of Adverse Events, Serious Adverse Events, and Adverse Device Effects, including Anticipated Adverse Device Effects and Unanticipated Adverse Device Effects.

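### Section VI tests efficacy on autistic traits only with one unblinded parent form and its subscales, gives the clinician ratings already collected no analysis, and plays down open-label bias because the trial is short

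*Combined protocol and SAP*

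**What the plan says.** The Study Design section describes the trial thus: "This study is a 10-week, open-label, single treatment group designed to investigate efficacy, safety and tolerability of tPBM". Under Sample Size in section VI, Biostatistical Analysis, the primary outcome is "reduction in ASD symptoms as measured by change in SRS-2 total raw score from baseline to endpoint". Section 1.2.2.1 describes the SRS-2 as "a 65-item rating scale completed by the parent used to measure the severity of autism spectrum symptoms". Under Primary Objective, section VI adds: "Secondary measures of efficacy for the treatment of ATs will be the SRS-2 subscales", and lists five of them. It names no other AT efficacy measure. The ADHD-SC serves only the ADHD objective.

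Other parts of the protocol give clinician ratings a larger place:

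- The background section, where it proposes the trial, says that "treatment response to tPBM will be monitored by parent- and clinician-rated measures during regularly scheduled visits".
- Study Assessment Scales and Forms counts the CGIs and GAF, taken at each visit, among the measures of efficacy as well as safety.
- Section 1.2.1.1 says "CGI scales will be used for the assessment of ADHD and ATs". It also describes the MGH-SECS-C as a clinician scale of change in ASD symptoms.
- Table I schedules the CGIs at every visit and the MGH-SECS-C at screening and Week 8.

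On bias, section VI argues that comparing participants with themselves balances static confounders. It concedes that dynamic factors can still bias the result and that this limitation comes with an open-label design. It then says: "However, we are confident that any such factors will have a minimal impact on this study considering the duration of the trial".

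**The concern.** The SRS-2 total and its subscales share items, rater and sitting. If they move together, that adds little evidence beyond the total. The parent knows that treatment is being given and takes part in giving it: at the Baseline Visit, staff instruct the subject's "parent/guardian on the administration of the tPBM such that the headband is appropriately placed". Expectancy in that rater would reach all the planned AT results at once.

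A second informant is already in the data but has no defined place in the analysis. One consequence is that whether and how to report the clinician AT ratings can be settled after the results are seen. Another is that a participant may qualify on CGI-AT severity of 4 or more without reaching an SRS raw score of 75, and then be evaluated for efficacy only on the parent form.

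The reassurance based on duration matters most, because it bears on what the trial may conclude. If it stands, a significant fall in SRS-2 can be presented as a treatment effect with the main rival explanations already set aside.

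**Working it through.** **Collected against analysed, for ATs**

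| Measure | Rater | When (Table I) | Analysis in section VI |
|---|---|---|---|
| SRS-2 total | Parent | Screening, Weeks 4, 8, 10 | Primary, mixed linear model on visit |
| SRS-2 subscales | Parent, same form | Same | Secondary, same model |
| CGI for ATs | Clinician | All visits | None named |
| MGH-SECS-C | Clinician | Screening, Week 8 | None named |

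Section VI does set out general model types for binary, count and normal outcomes, but ties none of them to the CGI or the MGH-SECS-C. Section 1.2.1.1 also lists a midpoint MGH-SECS-C, which appears neither in Table I nor in the Week 4 assessment list.

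**The duration argument.** A short trial does limit maturation and changes in circumstances. Two other time-varying sources are not limited in this way:

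- Rater expectancy can act from the first rating made on treatment.
- Regression to the mean needs only one repeat measurement. An SRS raw score of at least 75 is one entry route. Under Study Design, the higher of two forms decides eligibility when a second family member completes one. Table I shows no SRS-2 at Week 0, so the only pre-treatment column is screening, where selection takes place.

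**Reproducing the plan's power.** The inputs, from Sample Size, are n = 60, two-sided alpha 0.05, r = 0.5 and unit SD.

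- SD of change = √(2 × (1 − 0.5)) = 1.0.
- Power = P(|T| > t_crit), where T is noncentral t with 59 df and noncentrality d × √60 / SD of change.
- At d = 0.8, power is 99.998% (plan: 99.9%). At d = 0.37, it is 80.5% (plan: 80%).
- Enrolment: 60 / (1 − 0.33) = 90 (plan: 90).

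All the stated figures reproduce, and none is disputed.

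**Smallest significant change.** t_crit / √60 = 2.001 / 7.746 = 0.258, or about 0.26 SD.

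**No true effect, but a non-specific shift b in ratings.** The documents give no value for b, so these are assumptions.

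| b (SD) | Noncentrality b × 7.746 | Probability of p < 0.05 |
|---|---|---|
| 0.2 | 1.549 | 0.33 |
| 0.3 | 2.324 | 0.63 |
| 0.4 | 3.098 | 0.86 |

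For b = 0.3, the probability is 0.49 at r = 0.3 (SD of change 1.183) and 0.95 at r = 0.8 (SD of change 0.632).

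These are paired t-test figures, the basis that the plan uses for power. The planned analysis is a mixed-model slope over visits, so they are illustrative.

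**The case against.** The strongest reply is that this is an exploratory single-arm trial that admits its main weakness, and that the choice of secondary endpoints is partly preference. Much of this stands, and it rules out several stronger readings that a reader might infer.

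- *The clinician measures have no efficacy role.* The documents do not support this. Study Assessment Scales and Forms names the CGIs as efficacy measures, and section 1.2.1.1 describes the CGI in those terms. The gap is narrower: section VI gives CGI-AT and MGH-SECS-C no endpoint or analysis, which is inconsistent with those sections.
- *The plan ignores or flatly dismisses bias.* It does not. Section VI acknowledges the limitation and itself says that only static factors are balanced. It never names rater expectancy or regression to the mean. What fails is the step from short duration to minimal impact.
- *The plan would count the total and five subscales as six confirmations.* Nothing in section VI says so. There is one primary outcome, and subscales can properly describe which domains change. Section VI also states no success rule.
- *The 33%, 63% and 86% measure the fault of relying on a parent.* They do not. They describe any uncontrolled pre-post test of this size under the assumed shift, and would apply equally to a clinician scale on the same standardized assumptions.
- *Clinician ratings would independently corroborate the SRS-2.* They would not. The clinicians know the treatment and adjust its duration according to response (Devices and Dosing; Flexible Titration Schedule). CGI-AT is also an entry criterion, so regression to the mean can affect it too. Data Collection Forms mentions independent evaluators, but their role and blinding are defined nowhere.

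The inconsistency between sections and the unsupported reassurance both survive.

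**Conclusion.** The point holds in limited form and should be corrected. Section VI rests AT efficacy on one parent form and its subscales, while clinician AT ratings described elsewhere as response or efficacy measures are left without an analysis. Its ground for expecting minimal bias does not cover expectancy or regression to the mean.

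The size can only be illustrated. At n = 60 and r = 0.5, a change of 0.26 SD is enough for significance, and assumed non-specific shifts of 0.2 to 0.4 SD would give false positives in 33% to 86% of trials. The documents say nothing about how large such a shift would be. Adding clinician endpoints leaves these figures unchanged. Only the wording of the conclusion addresses them within the present design.

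**What to change.** 1. In section VI, replace the sentence that relies on duration. State that expectancy of unblinded parents and clinicians, and regression to the mean, cannot be separated from a tPBM effect in this design. State also that a significant SRS-2 change will be reported as pre-post improvement under open treatment, not as demonstrated efficacy.
2. Under Primary Objective, prespecify change in CGI-AT severity, and change in MGH-SECS-C from screening to Week 8, as supportive secondary AT measures. Give an analysis for each, describe them as coming from a second, also unblinded, informant, and attach no confirmatory claim. Label the SRS-2 subscales descriptive. This brings section VI into line with the background section and with Study Assessment Scales and Forms.
3. Reconcile the MGH-SECS-C schedule between section 1.2.1.1, which lists a midpoint, and Table I, which does not.

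The cost is wording and a few more models on data already collected, with no new visit, rater or form and no change in sample size. The drawback for the sponsor is a less favourable stated conclusion.
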